4.2.2.2. Secondary Outcome Analyses

Descriptive statistics will be used to describe the study population and characterize the clinical presentation of Post-Injection Syndrome events including outcome.

Adjusted odds ratios and 95% confidence intervals will be calculated using logistic regression to identify risk factors for patients experiencing Post-Injection Syndrome events.

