2.2. Secondary Objectives

The secondary objectives of this study are to:

- further characterize the clinical presentation, including the outcomes of Post-Injection Syndrome events
- identify potential risk factors associated with Post-Injection Syndrome events
- characterize hospitalization at baseline (previous 6- or 12-month) and postbaseline

3. Methods

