3.3.1. Assessment of Treatment Outcomes

Study enrollment will occur when the patient provides consent to release medical information. DCP 1 will occur at the first administration of olanzapine LAI after consent. The investigator will record all baseline information, including demographics, year of initial diagnosis of schizophrenia, all prior depot antipsychotic medication use, history of psychiatric drug use, and previous psychiatric hospitalization information.

The frequency of DCPs will depend on the frequency that the patient is receiving olanzapine LAI. Every administration of olanzapine LAI will be considered a DCP. If the patient is seen by study staff, but does not receive olanzapine LAI, this is not to be reported as a new DCP in the electronic data capture system. Any relevant observations made by the investigator or reported to the investigator are to be recorded on the appropriate data form (electronic case report form).

Data collected at every DCP will include all AEs, all current medications (including over-the-counter), recreational substance use in the past 24 hours (except for nicotine and caffeine use), mental status at the end of the observation period, date and time of injection, size of needle (length and gauge) used for injection, clinical setting of injection administration, dose, collection of the frequency of metabolic monitoring, and psychiatric hospitalization information. The frequency of metabolic monitoring is being collected to assess adherence to label or metabolic guideline recommendations. The actual lab results (if performed) will not be collected. These data collected at every DCP are summarized in Attachment B034.1.

More detailed data are to be recorded if the patient has a potential post-injection syndrome event, if applicable and if possible, such as date/time of event onset and date of event resolution

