4.1. Determination of Sample Size

Based on the patient retention rates of Study HGKB through 30 September 2007, it is anticipated that the approximately 5000 patients to be observed in Study B034 will experience at least 92,500 injections. Based on the estimated incidence by injection (0.072%) as of 15 July 2008, this number of injections will have at least 80% power to show the proportion of injections resulting in a Post-Injection Syndrome event (θ) is less than 0.10%. It is the intent of this study to show the rate of Post-Injection Syndrome events in olanzapine LAI to be less than 0.10%. More patients may need to be enrolled to ensure that at least 92,500 injections are administered.

Assuming a null hypothesis proportion θ_0 to be 0.072%, an exact binomial test with a nominal 0.05 two-sided significance level will have at least 80% power to detect the difference between θ_0 of 0.072% and the alternative proportion of 0.10% when the number of injections is 92,500. In terms of events per patient, assuming a null hypothesis θ_0 to be 1.36% (estimated incidence by patient as of 15 July 2008), this sample size will allow for at least 70% power to detect the difference between θ_0 and the alternative proportion of 2% at the 0.05 two-sided significance level.

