4.2.1.1. Study Population

All patients who provide consent to release information and who fulfill the study entry criteria will be included in the analyses. For those patients who are lost to follow-up, or who drop out of the study, the analyses will include all data up to the point of their last data collection. Due to the observational nature of this study, patients who violate the protocol will be included in the analyses.

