4.2.1.4. Adjustments for Covariates

Due to the observational nature of this study, covariate adjustments will be made to control for biases and confounding where appropriate.

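### The risk-factor model in Section 4.2.2.2 reads as one outcome per patient and does not say how the varying number of injections enters; odds ratios will be biased for any factor linked to injection count, and injection-level factors will be diluted

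*Protocol*

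**What the plan says.** The second secondary objective (Section 2.2) is to "identify potential risk factors associated with Post-Injection Syndrome events". Section 4.2.2.2 gives the method: "Adjusted odds ratios and 95% confidence intervals will be calculated using logistic regression to identify risk factors for patients experiencing Post-Injection Syndrome events". It names the model, the effect measure and patients as those who have the outcome. It does not mention number of injections, an offset, follow-up time or repeated records within a patient. The primary analysis in Section 4.2.2.1, by contrast, uses both a patient and an injection denominator.

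Exposure is not fixed. Section 3.3.1 says "The frequency of DCPs will depend on the frequency that the patient is receiving olanzapine LAI", and Section 4.2.1.1 says that for patients lost to follow-up or dropping out "the analyses will include all data up to the point of their last data collection". Section 3.2.3 lists an adverse event among the possible reasons for leaving observation.

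The candidate factors are captured at each injection. Section 3.3.1 lists "date and time of injection, size of needle (length and gauge) used for injection, clinical setting of injection administration, dose", together with current medications and recreational substance use in the preceding 24 hours.

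The one general safeguard is Section 4.2.1.4: "covariate adjustments will be made to control for biases and confounding where appropriate". Section 4.2.1 leaves further detail to the SAP.

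**The concern.** Section 1 attributes the event to what happens at one injection: partial entry into a vessel, vessel injury, or bleeding at the site. Each injection is therefore a separate opportunity for the event. A model with one row per patient raises two difficulties.

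- **Opportunity.** A patient with many injections has more chances of an event than a patient with few. Unless the model accounts for this, any characteristic that goes with more frequent injections or longer retention can look like a risk factor with no effect per injection.
- **Resolution.** Dose, needle, setting and recent substance use can differ between injections of the same patient. One row per patient forces them into a summary such as ever/never, which blurs the contrast between the injection that led to an event and the others.

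At stake is the credibility of the risk-factor objective: false leads on one side, and weakened or missed injection-level factors on the other.

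**Working it through.** **Inputs from the protocol (Section 4.1).** Rate per injection p = 0.072%; 5000 patients; 92,500 injections; rate per patient 1.36%. Mean injections per patient = 92,500 / 5000 = 18.5. Expected events = 92,500 × 0.00072 = 66.6.

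**Inputs that are assumptions.** The ratio of mean injections between patients with and without a factor, the spread of injection counts, the share of patients who stop after an event, and the prevalence of an injection-level factor. The protocol gives none of these.

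**The plan's own figures.** No figure is stated for the risk-factor analysis. The design inputs are coherent: 1 − (1 − 0.00072)^18.5 = 1.32%, close to the stated 1.36%. The exact two-sided binomial test of 0.072% against 0.10% with 92,500 injections has 82.5% power, which agrees with the stated 80% or more.

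**Step 1: a null factor, exposure left out.** With m injections at constant risk, P(event) = 1 − (1 − p)^m. Split the patients equally and keep the overall mean at 18.5:

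| Assumed ratio | Injections | Patient risks | Odds ratio |
|---|---|---|---|
| 1 | 18.5 vs 18.5 | 1.32% vs 1.32% | 1.00 |
| 1.2 | 20.2 vs 16.8 | 1.44% vs 1.20% | 1.20 |
| 1.5 | 22.2 vs 14.8 | 1.59% vs 1.06% | 1.50 |
| 2 | 24.67 vs 12.33 | 1.76% vs 0.88% | 2.01 |

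At ratio 2, for example, the odds are 0.01761/0.98239 = 0.01793 and 0.00884/0.99116 = 0.00892, and 0.01793/0.00892 = 2.01. Because the event is rare, the odds are close to m × p, so the odds ratio is close to the exposure ratio.

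**Step 2: how often this would look significant.** Simulation with 5000 patients, mean 18.5 injections and negative-binomial counts (dispersion 1.5, assumed), testing at two-sided 0.05. Without exposure, the null factor is significant in about 5% of studies at ratio 1, 36% at ratio 1.5 and 74% at ratio 2. Repeat simulations gave about 32 to 41% and 73 to 80% for the last two.

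**Step 3: does covariate adjustment cure it?** The same null factor, with log(number of injections) as an ordinary covariate in the patient-level logistic model:

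| Share stopping after an event (assumed) | OR at ratio 1.5 | OR at ratio 2 |
|---|---|---|
| None | about 1.0 | about 1.0 |
| Half | about 1.35 | about 1.6 to 1.7 |
| All | about 1.67 | about 2.4 |

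With half stopping, false positives are about 20% and 46%; with all stopping, about 53% and 92%. The reason is that an event then shortens the patient's own injection count. The freely estimated coefficient of log(n) is pulled down and exposure is under-corrected. If all stop, the adjusted odds ratio is further from 1 than the unadjusted one.

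In the same scenarios, an injection-level logistic model and a complementary log-log model with a log(n) offset (coefficient fixed at one) stayed at 0.98 to 1.02, with false-positive rates near the nominal 5%.

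**Step 4: a factor that varies between injections.** Assume it is present at 10% of injections and coded ever/never per patient.

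- No true effect: OR 2.83 without exposure, because more injections mean more chance of ever having the factor; 1.02 with log(n) and no stopping.
- True per-injection OR of 2: ever/never with log(n) gives 1.32; the injection-level model gives 1.95.

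The loss depends on the summary. Using the share of injections with the factor gave 1.78 when the truth was 2, but 0.76 when the truth was 1, so it is not a safe substitute.

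**The case against.** A reader might infer that the plan ignores exposure, cannot use injection-level factors, and will therefore produce confounded odds ratios. The case against that reading is good.

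- **Ignores.** The odds ratios are described as adjusted, and Section 4.2.1.4 promises control of confounding. Number of injections is an obvious covariate, and nothing excludes it.
- **Cannot use.** Injection-level factors can enter as patient summaries. The cost is dilution, not exclusion.
- **Will be confounded.** The bias needs a factor associated with injection count. At equal exposure there is none, and at a ratio of 1.2 the odds ratio is only about 1.2. The ratios are assumptions.
- **SAP detail.** The section does not literally say one record per patient, and offsets or clustering methods are ordinary SAP content.

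These points stand against the strong reading. They do not remove the corrected one. Section 4.2.2.2 does more than leave detail open: it names a method and a patient outcome that fit the question poorly. The general promise of adjustment is not a dependable cure either, because Step 3 shows the obvious way of honouring it failing once events shorten follow-up. The protocol gives no stopping rate, so how far it would fail is unknown. If patients stop, the injection count is partly a consequence of the event, which might seem to undermine an offset too; with the coefficient fixed at one, it did not.

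**Conclusion.** The point holds in a limited form. As worded, Section 4.2.2.2 is naturally read as a patient-level logistic model and does not say how differing injection counts are accounted for. Without an exposure term, a factor with no effect per injection acquires an odds ratio roughly equal to its exposure ratio: about 1.2, 1.5 and 2.0 at assumed ratios of 1.2, 1.5 and 2, and 1.0 at equal exposure. With log(injections) as an ordinary covariate, the bias disappears if nobody stops after an event; about 1.35 and 1.6 to 1.7 remain at ratios 1.5 and 2 if half do. Injection-level factors lose strength as patient summaries (1.32 against 1.95 for a true odds ratio of 2, at 10% prevalence and ever/never coding).

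The documents do not show that exposure will be ignored or that any particular factor will be biased, and the SAP may settle the matter. Only the rate per injection and the patient and injection totals come from the protocol. The consequence is confined to the risk-factor objective; the primary incidence estimate and the sample size do not depend on it.

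**What to change.** In Section 4.2.2.2, make the injection the unit of the risk-factor analysis. Suggested content: logistic regression with one record per injection, covariates as recorded at that injection, and within-patient dependence handled by GEE or cluster-robust standard errors. Odds ratios with 95% confidence intervals are kept as the measure. Repeat events look rare (39 events in 38 patients in Section 1), so the dependence correction should be small. With about 67 expected events, Firth-penalised estimation is a sensible sensitivity analysis and the number of covariates should be kept modest.

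If a patient-level model is also kept, use a complementary log-log or Poisson model with a log(number of injections) offset rather than log(injections) as a free covariate, and define the count explicitly. The text would then need to name the measure, since these models yield a hazard-type or rate ratio; for so rare an event it is numerically close to an odds ratio.

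The cost is a few sentences in the protocol or SAP and modest extra programming. The injection-level factors above are already collected at every data collection point, so no new data are needed.

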4.2.3. Health Outcome Analysis

Hospitalization at baseline (previous 6- or 12-month) and postbaseline will be tabulated for all enrolled patients. Descriptive statistics will be used to describe the frequency and duration of hospitalization.

4.2.4. Safety Analysis

Adverse event and serious adverse event (SAE) data will be summarized with descriptive statistics.

4.2.5. Subgroup Analyses

Subgroups may be identified and subgroup analyses conducted as deemed appropriate.

4.2.6. Interim Analyses

As this is an observational study, every 6 months AEs and SAEs are reviewed. In addition, the incidence of Post Injection Events are reviewed at least annually. Interim analyses will be conducted if deemed necessary at any time during the study.

5. Safety Evaluations

5.1. Adverse Events

The investigator or other study personnel will record via electronic data entry all adverse events (AEs) they become aware of arising in temporal association with Lilly drug(s) under evaluation as defined in this protocol. Additionally, personnel will record via electronic data entry any change in the condition(s) and/or the occurrence and nature of these AEs.

If an investigator becomes aware of AEs occurring to a subject after the subject's participation in the study has ended, the investigator should report the AEs to the sponsor. These AEs collected will be included in the Pharmacovigilance system of the sponsor.

Additionally, the investigator or other study personnel will record via study-specific SAE form the following safety information for Lilly drugs under evaluation, regardless of whether there is an associated adverse event:

- pregnancy exposures
- breast-feeding exposures
- overdoses
- misuse
- abuse
- medication error
- lack of drug effect
- off-label use
- suspected transmission of infectious agent

Investigators and other study personnel are requested to report adverse reactions in temporal association with Lilly drugs not under evaluation per this protocol or non-Lilly drugs to the appropriate party (for example, regulators or Lilly) as they would in normal practice as required by applicable laws, regulations, and practices. Standard postmarketing practices for reporting AEs to local regulatory bodies should also be followed for any AEs occurring in temporal association with the study drug.

The investigator or other study personnel will report to Lilly or its designee any **nonserious** adverse event arising in temporal association with the Lilly drug(s) under evaluation within 30 days of awareness of the event via a sponsor-approved method.

5.2. Serious Adverse Events

The investigator or other study personnel will report to Lilly or its designee any **serious** adverse event (SAE) arising in temporal association with the Lilly drug(s) under evaluation within 24 hours of awareness of the event via a Sponsor-approved method. Reports issued via telephone

are to be immediately followed with official notification on study-specific SAE forms. An SAE is any AE from this study that results in one of the following outcomes:

- death
- initial or prolonged inpatient hospitalization
- a life-threatening experience (that is, immediate risk of dying)
- persistent or significant disability/incapacity
- congenital anomaly/birth defect
- or is considered significant by the investigator for any other reason.
- For study purposes, all potential Post-Injection Syndrome events should be reported to Lilly, or its designee, as SAEs utilizing the reporting category of “Other” in case the event does not meet any other SAE criterion. Potential Post-Injection Syndrome events should be reported using the same procedure as all SAEs.

Important medical events that may not result in death, be life threatening, or require hospitalization may be considered serious adverse drug events (ADEs) when, based upon appropriate medical judgment, they may jeopardize the patient.

5.3. Complaint Handling

Lilly collects product complaints on study drugs and drug delivery systems used in medical research studies in order to ensure the safety of study participants, monitor quality, and to facilitate process and product improvements. Product complaints will be reported in the same way that any complaints on prescribed products are reported to the manufacturer.

6. Patient Consent to Release Information, Ethical Review, and Regulatory Considerations

6.1. Patient Consent to Release Information

This is an observational research program and does not impose any form of intervention on the investigator. Hence, the assessment and treatment of patients is based solely on the investigator's routine or usual practice in the provision of care to patients with schizophrenia.

As this is an observational study, the patient will provide authorization for the uses and disclosures of their personal health information as described in the study Consent to Release Information. This consent covers the collection and release of data regarding treatment and its outcomes for the entire period of the study. The confidential nature of the patient information will be maintained.

6.2. Ethical Review and Regulatory Considerations

Observational studies will be submitted to ethical review boards (ERBs) for approval whenever required by local law. In addition, regardless of local law, all prospective observational studies will be submitted to at least one ERB per country for review and to confirm that the study is considered noninterventional in that country. Regulatory authorities will be notified and approval sought as required by local laws and regulations. Progress reports will be submitted to ERBs and regulatory authorities as required by local laws and regulations.

This study will be conducted in accordance with the ethical principles that have their origin in the Declaration of Helsinki and that are consistent with good clinical practices and applicable laws and regulations of the country or countries where the study is being conducted, as appropriate.

7. Record Keeping, Data Reporting, Data Quality Assurance, and Publications

Patient data are to be recorded on simple, unambiguous data forms. Investigators are responsible for the integrity of the data (that is, accuracy, completeness, legibility, and timeliness) reported to Lilly. The investigator is to follow local laws and regulations or institutional practices for document retention. An electronic data capture system will be used in this trial. All data will be collected on a source document (for example, work sheet or patient chart) and will then be entered into the electronic data capture system by the investigator or his/her designee. These case report form data will be encoded and stored electronically on case report forms in a clinical trial database. Data from complaint forms submitted to Lilly will be encoded and stored in the global product complaint management system.

Informed Consent	X		
Demographics	X		
Height	X		
Weight	X	X	
Medical History Disease Characteristics, Psychiatric History	X		
Consumption Habits During the Study ^b	X	X	
Current Medical Status: Lab Event ^f	X	X	
Previous Therapy (Antipsychotics)	X		
Olanzapine Long-Acting Injection	X	X	
Mental Status Assessment at the End of the Observation Period	X	X	
Pre-existing Conditions, Adverse Events ^c	X	X	X ^d
Concomitant Therapy ^e	X	X	X
Current Medical Status: Post-Injection Syndrome Event			X
Study Adverse Events: 24 Hours Post Injection			X
Psychiatric Hospitalization Information ^g	X	X	X
Subject Summary	X	X	

Abbreviations: DCP=Data Collection Point

- a For purposes of electronic database collection only, a Data Collection Point (DCP) has the same meaning as a Visit within the electronic data capture system.
- b Current Consumption Habits are those recreational drugs that have been used or consumed within the previous 24 hours prior to the injection of olanzapine LAI. These substances include amphetamine/methamphetamine, barbiturate, cannabinoid, cocaine, hallucinogen, opiate, phencyclidine, and alcohol.
- c For Adverse Events occurring between Data Collection Points (DCPs), collect the event term, the start date, the stop date (if applicable), the severity, and the seriousness.
- d For Adverse Events occurring within 24 hours following an injection of olanzapine LAI, collect the start time of the event, event term, the start date, the stop date, the severity, and the seriousness. Within the source documentation, collect the date and time that the post-injection adverse event was resolved.
- e For Concomitant Therapy taken between Data Collection Points (DCPs), collect the treatment name, start date, the total daily dose, and the stop date (if applicable). For any Concomitant Therapy taken or prescribed specifically to treat post-injection adverse events, within the source documentation, collect the treatment name, start date and start time, the total daily dose, and the stop date and stop time (if applicable).
- f As there are no labs collected in this study, the Current Medical Status: Lab event form will collect the status of metabolic monitoring, the frequency of metabolic monitoring is being collected to assess adherence to label or metabolic guideline recommendations. The actual lab results (if performed) are not collected.
- g Psychiatric Hospitalization is defined as at least one overnight stay for psychiatric purposes.

Attachment 2. Protocol Amendment F1D-MC-B034(c) Post-Injection Syndrome in Patients with Schizophrenia Receiving Olanzapine Long-Acting Injection

Overview

Protocol F1D-MC-B034(c) Observational Study Description F1D-MC-B034(c) Post-Injection Syndrome in Patients with Schizophrenia Receiving Olanzapine Long-Acting Injection has been amended. The new protocol is indicated by amendment (c) and will be used to conduct the study in place of any preceding version of the protocol.

The overall changes and rationale for the changes made to this protocol are as follows:

- Correction of an inadvertent omission of a secondary objective. The global health outcome objective of characterizing hospitalization at baseline (previous 6- or 12-month) and postbaseline has now been added to Section 2.2. This measurement and its analysis were already described in Section 3.3.1 (Assessment of Treatment Outcomes), Section 4.2.3 (Health Outcome Analysis), and Attachment 1 (Data Collection Schedule).
- Correction to wording in Section 3.2.3 (Patient Discontinuation from Study). The word “Criteria” had inadvertently been used when what was intended was “Possible reasons.” The items listed do not represent criteria for automatic discontinuation but instead represent possible reasons that a patient might discontinue the study.
- Addition of updated required protocol template title page and text in Section 5.1 (Adverse Events) and Section 5.2 (Serious Adverse Events), including new text that states that investigators and other study personnel are requested to report adverse reactions associated with Lilly and non-Lilly drugs to Lilly as well as local regulatory bodies, as they would in normal practice as required by applicable laws, regulations, and practices.

Revised Protocol Sections

Note: Deletions have been identified by ~~strikethroughs~~.
Additions have been identified by the use of underscore.

